All patients receiving parenteral nutrition are followed by the Clinical Nutrition Service. Eligibility for the trial will be discussed on rounds. Prior historical and physical information, imaging studies, biopsies, and other available specialized tests will be reviewed by the multidisciplinary team experienced in the diagnosis and treatment of parenteral nutrition associated liver disease. Additional biochemical monitoring will be performed as necessary. If the patient's status supports consideration of treatment, the option for non-experimental therapy will be investigated. A similar process will be utilized for self-referrals and potential patients referred from distant healthcare facilities.

Soybean based Fat Emulsion (Intralipid[®] and/or Liposyn[®])

The conventional PN comparison group will be selected from patients previously studied by Andorsky et al.(31) We will study the subset of those patients whose recorded direct bilirubin was ever > 2 mg/dL. Information about these patients will be extracted from the Excel database used for this study and provided to us by the study's Principal Investigator, [name]. A request for research limited to the use of medical records/charts and computer databases was submitted and approved by the Committee on Clinical Investigations on January 17, 2007 (M07-01-0030).

Inclusion Criteria:

Andorsky et al. reviewed medical records of patients who were born at Children's Hospital Boston from 1985 to 1996 and who received a diagnosis of short bowel syndrome at most 30 days after birth (in the neonatal period). Short bowel syndrome was defined as dependence on PN for at least 90 days for diagnosis resulting from congenital intestinal malformations and/or intestinal resection.

Exclusion Criteria:

Patients with incomplete medical records (10 patients briefly seen for a second opinion) were excluded from the Andorsky et al. study. For our study, we will further exclude the subset of patients whose direct bilirubin was never > 2 mg/dL at any time during their follow-up times.

Follow up Study Utilizing Contemporary Historical Controls

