Patients in the proposed trial will be referred from the Children's Hospital Surgical Department, the NICU, or Clinical Nutrition Service. Patients with PNALD may also be referred from other healthcare facilities by their physicians or be self-referred. Approximately 5-10 patients/year are diagnosed with severe PN associated liver injury at CHB. The Principal Investigator ([name]) or Co-investigator ([name]) will discuss treatment options including study treatment with the patient (and parents or legal guardians in the case of a minor). Informed consent for participation in the study will only be obtained from these

physicians who are able to fully inform the patients of alternatives to participation. If the patient is a minor but of sufficient age and understanding, patient assent will also be obtained.

ii. WHAT recruitment methods and materials (e.g. posters, fliers) will be used? - *attach all materials*
none

iii. WHO will be responsible for subject recruitment?

No patients are recruited for this study. For patients that are referred for further consideration, the Principal Investigator ([name]) or Co-investigator ([name]) will discuss treatment options including study treatment with the patient (and parents or legal guardians in the case of a minor).

Soybean based Fat Emulsion (Intralipid® and/or Liposyn®)

Subjects for the Andorsky et al. study were identified based on: 1) International Classification of Diseases, Ninth Revision code of 579.3 (post-surgical malabsorption, commonly used to code short bowel syndrome); 2) review of the list of patients receiving PN at home who were followed by the Clinical Nutrition Service at Children's Hospital Boston; and 3) survey of attending surgeons, gastroenterologists, and nutrition physicians at Children's Hospital Boston.

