Additional comparisons across treatment periods for subjects receiving Omegaven® will be aimed to assess occurrence of spontaneous bleeding (e.g., unexplained bruising, oozing from gums/incision sites), and maximum triene/tetraene ratio, minimum platelets, and maximum international normalized ratio (INR), trends in pre-albumin (age standardized levels). We will also explore trends in coagulopathies based on curves of platelets, prothrombin time (PT), partial thromboplastin time (PTT) over time, and INR. We will also describe the rate with which INR ratios were > 2 (number of days/follow-up time), as a marker of coagulopathies.

Additional comparisons between Omegaven® and soybean oil fat emulsion groups will be performed with regards to rate in which albumin is > 3 g/dL, maximum triglyceride level, rate of blood stream infections (number of positive blood cultures/follow-up-time under PN after baseline), rate of central venous catheter (CVC) infections (number of CVC infections/follow-up time and number of gram positive CVC infections/follow-up time), and occurrence of anaphylactic reactions after baseline.

Nutritional outcomes between Omegaven® and soybean oil fat emulsion groups that will be compared include changes in weight- and height-for-age Z-scores from baseline to 10% PN or cessation of PN..

We will describe trends over time for all outcomes associated with fatty acid profiles (including triene/tetraene ratios, triglycerides, total omega-6 fatty acids, total omega-3 fatty acids, total saturated, total monounsaturated, and total polysaturated fatty acids). Specific fatty acids such as arachidonic, palmoleic, palmitic, oleic, stearic, and linoleic fatty acids will also be evaluated and described. Also, for exploratory purposes, we will compare the trend in weight- and height-for-age Z-scores between both groups.

2. Omegaven®

3. The patient will complete treatment with Omegaven® in this study when he/she is completely off PN, develops a contraindication for further use, or the patient/family requests to be removed from the study.

f. Data Collection Methods, Assessments and Schedule

Omega-3 Fat Emulsion (Omegaven™)

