Data will be collected by the PI (MP), the managing co-investigator (KG), and the clinical coordinator with the assistance of the nursing unit liaisons and research assistants in [name] laboratory. Hospital charts will be reviewed for pertinent clinical information. Results of liver biopsies and blood chemistries will be obtained from PowerChart within the Cerner computer system at CHB. Specifically, the history of present illness, past medical history, and birth history, pertinent physical exam findings including patient weight, the results of liver biopsies, and parenteral and enteral feeding history will be collected. The information will be recorded on hard copy data collection forms.

Soybean based Fat Emulsion (Intralipid® and/or Liposyn®)

Data will be extracted from the Excel spread sheet used to store data of the Andorsky et al. study. Additionally, we will obtain information about date of birth (to estimate age at each visit and nutritional safety outcomes) and blood transfusions in Power Chart within the Cerner computer system at CHB. In the original study performed by Andorsky et al., data was abstracted from charts, nursing flowsheets (for nutritional intake data), and outpatient visit notes in two week intervals.

g. Study Timeline (as applicable)

This study will end when the results of an FDA approved clinical trial proves Omegaven® treatment to be ineffective or the product is approved for use in the United States. The investigators proposal to the Orphan Products Grants Program of FDA submitted in spring 2007 which was accepted.

h. Adverse Event Criteria and Reporting Procedures

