Adverse events (AEs) will be assessed and reported from the time of the first Omegaven® infusion until exit from the study in accordance with CHB Committee on Clinical Investigations (CCI) reporting requirements. In particular, the patient will be observed during and shortly after Omegaven® administration for the occurrence of anaphylactic or allergic reactions. Other expected adverse events include death, blood stream infection; transfer to ICU for treatment of respiratory distress or hemodynamic instability; re-hospitalization for treatment of blood stream infection, dehydration, electrolyte abnormalities, catheter malfunctions, bowel obstructions, and urinary tract infection. Unexpected adverse events will also be assessed and reported in compliance with the CHB CCI requirements. Patients experiencing any adverse events that are moderate or severe in nature and that may be related to Omegaven® will have their treatment temporarily halted until the adverse event has resolved. Dose modifications will occur as described above. If a dose reduction is made for adverse events later considered to be unrelated to Omegaven®, the Omegaven® dose will be increased back to the dose prescribed prior to the dose reduction. Patients with anaphylactic or allergic reactions will not continue Omegaven® treatment.

Any serious or unsuspected adverse events will be reported to the Committee on Clinical Investigation (CCI) and the FDA within 72 hours of the occurrence of being known, or immediately if the event is fatal or life threatening as per Children's Hospital Policy on Adverse and Unexpected Events and Unanticipated Risks to Research Subjects and Others. This will be done in person, by telephone, or email, and by completion of the CCI's form for adverse/unexpected event reporting.

Adverse events are detected by CHB acute care medical and nursing staff during provision of standard care services including the routine monitoring of vital signs and daily physical exam data. Adverse events identified by CHB staff are reported to the Principal Investigator immediately by telephone or pager, and subsequently to the appropriate board or committee.

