Outpatient/on Omegaven®	Direct bilirubin ≥ 2 mg/dL	PN profile, AST, GGT, CRP, lipid Panel, PT, PTT, INR, fibrinogen, EFA Panel	Weekly
	Direct bilirubin ≤2mg/dL	PN profile, AST, GGT, CRP, lipid Panel, PT, PTT, INR, fibrinogen, EFA Panel	Monthly until off Omegaven and at least 1 direct serum bilirubin < 2 mg/dL

*minimum requirements, may be performed more frequently for routine clinical care

If under the discretion of the principal investigator the patient is able to return home and receive Omegaven®, the patient is required to return to Boston every 2 months or other mutually agreed upon schedule for evaluation and follow up. The Principle Investigator also requires for arrangements to be made through the patient's home health care agency for the required weekly or monthly blood draws the patient will need while at home in order to remain on Omegaven®. The lab results then must be faxed to Children's Hospital Boston in a timely manner. Additionally, measures will be taken to decrease the chance of administration errors when Omegaven® is given in the home. Families will be provided with a letter outlining strategies for reducing medication administration errors, such as independent double-checks. Also, families will be provided with fish stickers to be affixed to their Omegaven® pump to decrease the likelihood of using the incorrect pump to administer Omegaven®.

Dose reduction will occur if there is evidence of lipid intolerance (serum triglycerides > 200mg/dL) or evidence of bleeding. Growth indices include weight, length, and head circumference will also be monitored.

Other standard care laboratory results will be captured for the Omegaven® protocol. These are listed along with the standard schedule in Table 3.

The frequency of laboratory monitoring may be reduced to monthly or as clinically necessary, for patients who have been on a stable regimen of Omegaven® for a minimum of 4 months and whose serum bilirubin and hepatic enzymes have normalized.

The CAIR team completes rounds every Wednesday morning on all inpatient short bowel patients which incorporates all Omegaven® study patients. A complete comprehensive case review for all inpatients receiving Omegaven® therapy under the compassionate-use protocol and any outpatients issues are discussed among the CAIR team and with [name], [name], and the Omegaven® study nurses. All pertinent medical, nutritional, and psychosocial outpatient information is reviewed during these case reviews.

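### Infections and adverse events away from Children's Hospital Boston have no defined capture route, yet that time counts in the infection rates: the absolute Omegaven rate can be understated, with uncertain effect on the comparison with controls

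*Combined protocol and SAP*

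**What the plan says.** **Detection and data sources.** Under Adverse Event Criteria and Reporting Procedures, "Adverse events are detected by CHB acute care medical and nursing staff during provision of standard care services", by way of vital signs and daily examinations. The same section has events assessed from the first infusion until study exit. For the Omegaven group, Data Collection Methods states "Hospital charts will be reviewed for pertinent clinical information" and "Results of liver biopsies and blood chemistries will be obtained from PowerChart within the Cerner computer system at CHB". Data Management Methods has all data abstracted from medical records.

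**Where patients are.** Recruitment Methods states "Patients with PNALD may also be referred from other healthcare facilities by their physicians or be self-referred". Under the Data and Safety Monitoring Plan, a patient may receive Omegaven at home, and then "the patient is required to return to Boston every 2 months or other mutually agreed upon schedule". Between visits, results of the weekly or monthly draws must be faxed to the hospital. The listed panels do not name blood cultures.

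**How infection is measured.** The Treatment safety endpoints include "rate of blood stream infections (number of positive blood cultures/follow-up-time under PN after baseline" and, for central venous catheter (CVC) infections, "number of CVC infections/follow-up time and number of gram positive CVC infections/follow-up time". Neither denominator is limited to time under observation. Transfusion is different: the Data Analysis Plan compares proportions.

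**Controls.** For the first historical cohort, "Patients with incomplete medical records (10 patients briefly seen for a second opinion) were excluded from the" study. The 1999-2004 cohort has no such exclusion. Lists of home PN patients were used to identify both cohorts.

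**The concern.** The numerator of the infection rate depends on what reaches the hospital's staff and charts, while the denominator runs on regardless of where the child is. The protocol itself lists blood stream infection and re-hospitalisation as expected events, and for a child living far from Boston a local hospital may well manage them.

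Three uses of the data are exposed:

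- the safety summary, which is primarily descriptive and so rests on absolute rates;
- hypotheses 2.3 (infection) and 2.4 (transfusion), which predict lower values on Omegaven, the direction in which missed events push that group's figures;
- the DSMB's six-monthly review, which cannot weigh events it never receives.

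The Missing Values section expects nearly complete data, particularly for safety. Potential Study Limitations discusses reporting changes over the years and missing control data, but not events treated elsewhere.

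**Working it through.** **The plan's own figures.** The documents give no infection rate, no share of follow-up spent off site and no capture fraction, so there is no stated figure to reproduce. The values of f and c below are assumptions.

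**1. Absolute rate in one group.** Let f be the share of follow-up away from the hospital and c the share of off-site events that reach the study record. With a constant true rate:

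observed rate / true rate = (1 - f) + f·c = 1 - f(1 - c)

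| f | c = 0 | c = 0.5 | c = 0.75 | c = 1 |
|---|---|---|---|---|
| 0.25 | 0.75 | 0.875 | 0.9375 | 1 |
| 0.50 | 0.50 | 0.75 | 0.875 | 1 |
| 0.75 | 0.25 | 0.625 | 0.8125 | 1 |

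The size depends on f, c and the constant-rate assumption. The direction does not: missed events leave the numerator while the denominator stays put, so the ratio cannot exceed 1.

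**2. Comparison with controls.** With equal true rates, and O for Omegaven and C for controls:

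observed ratio = [1 - fO(1 - cO)] / [1 - fC(1 - cC)]

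Take fO = 0.5 and cO = 0.6, so the numerator is 1 - 0.5 × 0.4 = 0.80.

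| Assumption for controls | Denominator | Observed ratio |
|---|---|---|
| Complete capture | 1.00 | 0.80 / 1.00 = 0.80 |
| fC = 0.25, cC = 0.6 | 1 - 0.25 × 0.4 = 0.90 | 0.80 / 0.90 = 0.89 |
| fC = 0.5, cC = 0.6 (same as Omegaven) | 0.80 | 1.00 |
| fC = 0.5, cC = 0.4 | 1 - 0.5 × 0.6 = 0.70 | 0.80 / 0.70 = 1.14 |

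The ratio falls on either side of 1, and nothing in the documents selects a row.

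**3. Outcomes without a time denominator.** Transfusion is analysed as a proportion, so these formulas do not apply. A patient whose only transfusion took place elsewhere and was missed would still be counted as not transfused. No general denominator is given for adverse events; there the effect is on the counts.

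**The case against.** The strongest reply is that the sources are wider than a strict reading suggests. The chart-review sentence does not say the charts are only this hospital's, and the PowerChart sentence covers biopsies and chemistries, not infections. The confidentiality provisions list summaries of hospital admissions during the study, without restricting them to one site. The investigators review all Omegaven patients at least monthly, and the intestinal rehabilitation team discusses outpatient information weekly. All of this stands, and it makes very low capture less likely. But it describes discussion of what is already known and inspection of what is already held. It sets no routine enquiry, no record request and no rule for unobserved time.

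A reader might go further and infer that Omegaven rates are biased low relative to controls, and that false-positive differences follow. The documents do not support that:

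- Controls also spent time on home PN, and the soybean administration section describes discharge home.
- Control transfusions are taken from the same hospital system.
- The limitations section expects more missing data in historical controls.
- The incomplete-records exclusion covers ten brief second-opinion patients in one cohort only.

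Some features do point towards fuller capture in the first cohort: birth at the hospital, and outpatient notes abstracted at two-week intervals. They make an asymmetry possible without establishing it.

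**Conclusion.** The point holds for the absolute Omegaven infection rates. As written, the plan can count time in which events are not systematically sought, and any missed event understates those rates. Missed events can also lower the proportion transfused and the adverse-event counts sent to the DSMB. Under the assumed values (f from 0.25 to 0.75, c from 0 to 0.75), the observed rate lies between 0.25 and 0.94 of the true rate. The low end requires that no off-site event is captured, which the case reviews make unlikely.

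For the comparison with controls, the conclusion is limited to uncertainty of direction: 0.80 to 1.14 across the four cases shown, at a true ratio of 1. No false-positive rate can be attached, since it would require off-site shares, capture fractions and infection frequencies that the documents do not give. The outcomes affected are safety and secondary ones, in a non-randomised study that already names non-comparability as its main limitation. The change is worth making because it improves the data whichever way the net bias runs.

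**What to change.** 1. **Capture.** Add one fixed question to each existing home-laboratory contact and return visit: any outside admission, positive blood culture, transfusion or bleeding since the last contact? When the answer is yes, request the outside record.
2. **Time at risk.** For infection rates, count events and time only over intervals for which documentation is held, by the same rule in the Omegaven group and both control cohorts. A documented negative answer should count as documentation; otherwise outside time would enter only when an event had occurred. State how a reported event is handled when its record cannot be obtained.
3. **Reporting.** Give the share of follow-up away from the hospital in each cohort, where known. Add a sensitivity analysis limited to time or patients managed at the hospital.
4. **Limitations.** Add off-site under-capture to Potential Study Limitations as a bias of uncertain direction for the between-group comparison.

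Under a constant true rate, restricting time at risk to fully captured intervals brings the observed-to-true ratio in step 1 of the working to 1. If risk differs between home and hospital, the restricted rate describes the observed time only, which is why the off-site share should be shown. The cost is one question on existing contacts, the record requests, a few lines in the analysis plan, and some person-time lost where records cannot be obtained. Controls can be handled only from what was abstracted or remains in the charts.
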